#### 9.1.1.2. Secondary Estimand

The secondary estimand is DLT rate estimated based on data from DLT-evaluable participants in Part 2A and Part 2C during the DLT observation period. It is defined by the following attributes:

- Population: RRMM participants, as defined by the inclusion and exclusion criteria to reflect the targeted population of the treatment and either experience DLT(s) during the DLT observation period or complete the DLT observation period without DLT. Participants without DLTs who receive less than the planned doses of the study intervention are not evaluable for DLTs.
- Variable: Occurrence of DLTs during the DLT observation period.
- Treatment condition: At least 1 dose of study intervention of elranatamab.
- Population-level summary measure: DLT rate defined as the number of DLT-evaluable participants with DLTs in the DLT observation period divided by the number of DLT-evaluable participants.

## 9.2. Analysis Sets

For purposes of analysis, the following analysis sets are defined for Part 1 and Part 2, respectively.

Participant Analysis Set	Description
Safety Analysis Set	All enrolled participants who receive at least 1 dose of study intervention.
DLT Evaluable Set	All enrolled participants in Part 2A and Part 2C who received the planned 2 doses of 116 mg or 152 mg of study intervention during the DLT observation period or who received at least 1 dose of 116 mg or 152 mg of study intervention and experience DLT(s) during the DLT observation period.
PK Analysis Set	The PK analysis set will include all participants in the safety analysis set who have at least 1 postdose concentration measurement.  The PK parameter analysis set will include all participants in the safety analysis set who have at least 1 of the PK parameters of interest for eh-anatamab.
CCI	[Redacted]
Immunogenicity Analysis Set	tested for ADA. [Redacted]
CCI	[Redacted]

Note: "Enrolled" means a participant's, or his or her legally authorized representative's, agreement to participate in a clinical study following completion of the informed consent process and was assigned to treatment. Potential participants who are screened for the purpose of determining eligibility for the study, but do not participate in the study, are not considered enrolled, unless otherwise specified by the protocol.

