### 4.3.3. Definition of DLT (Part 2A and Part 2C)

Severity of AEs will be graded according to NCI CTCAE version 5.0. The severity of CRS and ICANS will be assessed according to the modified grading described by ASTCT. The DLT observation period will be 28 days starting from the first 116 or 152 mg dose.

A participant is classified as DLT-evaluable if they meet either criterion:

- Experiences a DLT during the DLT observation period,
- In the absence of a DLT, receives the planned number of doses at the planned dose level of the study intervention and receives scheduled safety assessments during the DLT observation period.

If a participant does not meet these criteria, he/she may be replaced.

For the purpose of RP2D determination, additional late toxicities in the context of all safety data available will also be considered. Safety information from any participants that do not meet DLT-evaluable criteria could still be considered for overall dose determination decisions.

As described in Table 5, any of the following AEs observed within the DLT observation period and considered related to study intervention will be classified as DLTs. Participants experiencing a DLT may resume dosing only if adequate recovery is achieved within the allowed time window and if permitted for the specific toxicity (see Sections 6.5.1 and 6.5.1.2).

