### 6.1.1. Elranatamab

Qualified and trained investigator site personnel will administer eh-anatamab to participants by SC injection. Ideally, each injection may be up to 2 mL in volume; however, if the maximum volume allowed per institution's policy is lower than 2 mL, the number of injections may be increased to accommodate this difference in volume and ensure the correct dose is delivered. If more than one injection is needed, these injections should be

administered within 2-3 minutes from each other. See [Appendix 9](#) for details on administration of multiple injections to the abdomen. Elranatamab should be administered to the abdomen, with preference given to the lower quadrants when possible.

A minimum of 2 days should be maintained between the 2 step-up priming doses (C1D1 and C1D4), a minimum of 3 days should be maintained between C1D4 and the first full dose (C1D8); a minimum of 6 days should be maintained between doses thereafter.

The windows for the different administration schedules are -1/+3 days for C1D4, C1D8 and then  $\pm 3$  days for QW and Q2W and  $\pm 6$  days for Q4W or **CCI**. Study staff should refer to the IP Manual for specific instructions on the handling, preparation and administration volumes of study intervention.

Dose modifications may occur according to the guidelines described in Section 6.5.

If the dose interval is changed, cycles will remain the same length (ie, 28-day cycles).

Each participant should receive study intervention until confirmed disease progression, unacceptable toxicity, withdrawal of consent, or study termination.

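### For participants without a DLT, the DLT Evaluable Set asks only for two higher doses and omits the window completion required by the estimand and the safety assessments required by Section 4.3.3

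*Protocol*

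**What the plan says.** Three places in the protocol say who is evaluable for DLT; SAP 4 repeats one of them.

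- **Protocol 9.2 and SAP 4 (analysis set).** A participant without a DLT qualifies as one "who received the planned 2 doses of 116 mg or 152 mg of study intervention during the DLT observation period". A participant with a DLT qualifies as one "who received at least 1 dose of 116 mg or 152 mg of study intervention and experience DLT(s) during the DLT observation period".
- **Protocol 9.1.1.2 (secondary estimand).** The population is those who have a DLT in the window or who "complete the DLT observation period without DLT". It adds: "Participants without DLTs who receive less than the planned doses of the study intervention are not evaluable for DLTs".
- **Protocol 4.3.3 (DLT definition).** The no-DLT criterion has two parts: "In the absence of a DLT, receives the planned number of doses at the planned dose level of the study intervention", and that the participant "receives scheduled safety assessments during the DLT observation period".

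Section 4.3.3 also fixes the window: "The DLT observation period will be 28 days starting from the first 116 or 152 mg dose".

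The 9.2 / SAP 4 set is the one used. Protocol 9.3.3.1 and SAP 6.2.1 run the DLT analysis on it. Protocol 9.5.2 and SAP 5.1.1.2 count the minimum of 6 evaluable participants per dose level by it. Nothing in either document reconciles the definitions.

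**The concern.** Among the visible secondary endpoints, the DLT rate is the only one given an estimand. The population in that estimand is not the population to be analysed. The analysis set omits observation through the window, so someone who received both doses and then ceased to be fully observed enters the denominator as a non-event. SAP 5.3 evaluates data as observed without imputation, so nothing later corrects this.

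Late observation matters for this endpoint. Some DLTs in Table 5 depend on duration, such as Grade 4 neutropenia lasting more than 5 days, and cannot be established without follow-up after dosing.

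The protocol applies the stricter principle elsewhere. Under the temporary-hold rules (9.4.1, notes to Tables 9 and 10), a participant without an event is evaluable only after at least 28 days of follow-up from first dose.

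At stake is a descriptive DLT rate by dose level that is still to be reported, and whether its denominators will agree with the evaluable numbers already stated in Protocol 4.1.

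**Working it through.** **1. Conditions for a participant without a DLT**

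| Source | Planned higher doses | Window completed | Scheduled safety assessments |
|---|---|---|---|
| Protocol 9.2, SAP 4 | yes | not stated | not stated |
| Protocol 9.1.1.2 | yes | yes | not stated |
| Protocol 4.3.3 | yes | not stated | yes |

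The two extra conditions are split: no single place states both. All three definitions exclude a no-DLT participant who missed a higher dose, so only participants who received both doses are affected.

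**2. The DLT branch does not differ.** The window opens with the first higher dose, so anyone with a DLT inside it has had at least one such dose. The definitions can differ only in the number of non-events.

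**3. Direction.** With D participants with DLTs, N evaluable under a stricter rule and k extra non-events admitted by the looser set, the rate changes from D/N to D/(N + k). Since k ≥ 0, the rate falls or stays the same.

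**4. Days at issue.** The window is 28 days and Q2W dosing gives 28/14 = 2 doses, on about Day 1 and Day 15. The Q2W dosing window in Protocol 6.1.1 is ±3 days, so dose 2 falls on Day 12 to 18. Days left after dose 2:

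- 28 − 12 = 16
- 28 − 15 = 13
- 28 − 18 = 10

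**5. Who is affected.** Death, withdrawal of consent or loss to follow-up after dose 2 ends observation. Starting new anticancer therapy ends recording of nonserious AEs (Protocol 8.3.1, 8.3.1.2), although SAEs continue to be recorded. Stopping study treatment alone does not end observation (see the objection).

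**6. Size.** Protocol 4.1 reports:

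- Dose level 1: 12 treated, 7 evaluable, one DLT event
- Dose level 2: 11 treated, 7 evaluable, one DLT event

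The rate is 1/7 = 14.3% at each level. The documents do not say which definition produced the 7s, so there are two cases:

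- If they are 9.2 counts, removing one incompletely observed participant gives 1/6 = 16.7%.
- If they are stricter counts, the 9.2 set adding one such participant gives 1/8 = 12.5%.

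If no two-dose participant was incompletely observed, k = 0 and the rate stays at 14.3%. The effect on the BLRM probabilities in Table 13 cannot be checked, because the visible text does not give the prior parameters.

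**The case against.** The strongest case against the point has four parts.

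**Stopping treatment does not end observation.** Protocol 7.1 keeps a participant who discontinues in the study for safety evaluation. Section 8.3.1 collects AEs for at least 90 days after the last dose, and the Part 2 schedule has a follow-up visit 28 to 35 days after the final dose with hematology and chemistry. This stands. A reader might infer that anyone who leaves treatment after dose 2 is unobserved. The documents do not support that: the gap is confined to the routes in step 5 of the working, and it is partial.

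**The gap from 4.3.3 alone is small.** In the visible Part 2 schedule, the Cycle 2 neurologic examinations fall on Days 1 and 15, the dosing days. Apart from continuous AE monitoring, no fixed safety visit appears between C2D15 and C3D1. A two-dose participant has therefore largely met 4.3.3. This also stands, and it makes the estimand's completion condition the one that matters more. The estimand's dose sentence does not remove that condition; it adds to it.

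**Large shifts are not shown.** A reader might set the single DLT against all treated participants and obtain 1/12 (8.3%) and 1/11 (9.1%). That assumes the 7s are strict counts and that every non-evaluable participant received both higher doses. Section 9.5.2 ties evaluability to 9.2, which suggests the 7s may already be 9.2 counts. Drop-out in Cycle 1 or a skipped Day 15 dose would also make a treated participant non-evaluable under every definition.

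**Little remains to be decided.** Enrollment is complete, the RP2D is selected, and Part 2C will not be explored. Dose decisions also drew on late toxicities, safety data from non-evaluable participants and other evidence (4.3.3, 9.5.2). The posterior was to be evaluated only after each cohort completed the window. That last provision sets timing; it does not remove an individual who left early. Otherwise this part stands and limits the severity.

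**Conclusion.** The mismatch is real and the fix is cheap, but the point is minor. The plan as written analyses the DLT rate on a set looser than its own estimand, and the difference can only lower the rate or leave it unchanged.

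The size cannot be determined from the documents. For one affected participant at a dose level, the rate moves from 14.3% to 16.7% if the 7s follow 9.2, or to 12.5% if they follow a stricter rule. Both figures rest on the counts in Protocol 4.1 and on the assumption that exactly one such participant exists. None is documented, so the shift may be zero.

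A reader might infer that the RP2D choice was affected, particularly since 1/6 lies above the 0.16 lower limit of the target-toxicity interval and 1/7 lies below it. The documents do not support this. Dosing decisions used posterior probabilities and other evidence rather than the raw rate, and no misclassified participant is shown.

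**What to change.** In SAP 4, and in Protocol 9.2 at the next amendment, define the no-DLT branch as: received the planned higher doses **and** completed the 28-day DLT observation period with the scheduled safety assessments. This matches 4.3.3 and 9.1.1.2 together. Leave the DLT branch unchanged.

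State which definition produced the 7 and 7 in Protocol 4.1, check the reported denominators against them, and list any two-dose participant with incomplete observation.

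The cost is one sentence in each document and a short listing. No new data and no change to treatment are needed. The denominator may be slightly smaller and the DLT rate slightly less favourable.

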## 9.3. Statistical Analyses

The SAP will be developed and finalized before any analyses are performed and will describe the analyses and procedures for accounting for missing, unused, and spurious data. This section is a summary of the planned statistical analyses of the primary and secondary endpoints.

### **9.3.1. General Considerations**

Unless otherwise specified, all analyses will be performed for each part (Part 1, Part 2) separately and for Part 1 and Part 2 combined. All efficacy analyses and safety analyses will be performed using the Safety Analysis Set.

No formal statistical testing will be conducted on this study. In general, descriptive summaries will be presented for the efficacy and safety variables collected. Continuous variables will be summarized using mean, standard deviation, minimum, median, and maximum. Qualitative variables will be summarized by frequency counts and percentages. Unless otherwise specified, the calculation of proportions will include the missing category. Therefore, counts of missing observations will be included in the denominator and presented as a separate category. Time to event variables will be summarized using Kaplan-Meier estimates (product-limit estimates) together with a summary of associated statistics including the median time with 2-sided 95% CIs. Probabilities of an event at particular time points may be estimated with corresponding 2-sided 95% CIs.

### **9.3.2. Primary Endpoint/Estimand/Analysis**

#### **Grade $\geq 2$ CRS rate during C1**

The primary endpoint for Part 1 & Part 2 combined is Grade  $\geq 2$  CRS rate during C1, defined as the proportion of participants in the Safety Analysis Set experiencing Grade  $\geq 2$  CRS as assessed by ASTCT criteria.

The median and its corresponding 2-sided 90% credible interval based on the posterior distribution of Grade  $\geq 2$  CRS rate will be calculated. In addition, point estimates of Grade  $\geq 2$  CRS rate will be calculated along with the 2-sided 90% CIs using the Clopper-Pearson method (exact CI for a binomial proportion).

### **9.3.3. Secondary Endpoints/Estimands/Analyses**

#### **9.3.3.1. Secondary Safety Endpoint**

##### **Incidence of DLTs (Part 2A and Part 2C only)**

The number and proportion of participants experiencing DLTs during the DLT observation period will be summarized and listed by dose level. Analyses of DLT will be performed on DLT Evaluable Analysis Set (as defined in Section 9.2).

#### **Overall Safety Profile and Tolerability**

AEs as characterized by type, frequency, severity, timing, seriousness, and relationship to elranatamab (Part 1 and Part 2). Laboratory abnormalities as characterized by type, frequency, severity and timing.

AEs (except CRS and ICANS) will be graded by the investigator according to NCI CTCAE v5.0 and coded using MedDRA. CRS and ICANS will be assessed according to the ASTCT criteria (See [Appendix 13](#)) and coded using MedDRA. AEs will be presented with

and without regard to causality based on the investigator's judgment. The frequency of overall toxicity, categorized by toxicity Grades 1 through 5, will be described.

Additional summaries will be provided for AEs that are observed with higher frequency and for AESIs identified in Section 8.3.8.

Clinical laboratory data will be classified by grade according to NCI CTCAE v5.0 and will be analyzed using summary statistics. The worst on-treatment grades during the treatment period will be summarized. Shifts in toxicity grading from baseline to highest grade during the on-treatment period will be displayed. Results for laboratory tests that are not part of NCI CTCAE will be presented as below, within, or above normal limits. Only participants with post-baseline laboratory values will be included in these analyses. Further details of analyses for all the laboratory parameters will be provided in the SAP.

### **9.3.3.2. Secondary Efficacy Endpoints**

#### **Objective Response Rate**

ORR is defined as the proportion of participants in the Safety Analysis Set with an objective response per IMWG response criteria as determined by investigator.

#### **Complete Response Rate**

CRR is defined as the proportion of participants in the Safety Analysis Set with a BOR of confirmed sCR/CR per IMWG response criteria as determined by investigator.

Point estimates of CRR will be calculated along with the 2-sided exact 95% CIs using the Clopper-Pearson method.

#### **Duration of Response**

DOR is defined, for participants with an objective response per IMWG criteria, as the time from the first documentation of objective response that is subsequently confirmed, until confirmed PD per IMWG criteria, or death due to any cause, whichever occurs first.

DOR will be censored on the date of the last adequate disease assessment for participants who do not have an event (PD or death due to any cause), on the date of the last adequate disease assessment before the new anti-cancer therapy for participants who start a new anti-cancer therapy prior to an event, or on the date of the last adequate disease assessment before the 2 or more missing disease assessments for participants with an event after 2 or more missing disease assessments.

DOR will be summarized using Kaplan Meier method and displayed graphically. Median DOR and 2-sided 95% CI (based on the Brookmeyer-Crowley method) will be provided.

### **Duration of Complete Response**

DOCR is defined, for participants with a BOR of confirmed sCR/CR per IMWG criteria, as the time from the first documentation of sCR/ CR that is subsequently confirmed, until confirmed PD per IMWG criteria, or death due to any cause, whichever occurs first.

DOCR will be censored on the date of the last adequate disease assessment for participants who do not have an event (PD or death due to any cause), on the date of the last adequate disease assessment before the new anti-cancer therapy for participants who start a new anti-cancer therapy prior to an event, or on the date of the last adequate disease assessment before the 2 or more missing disease assessments for participants with an event after 2 or more missing disease assessments.

DOCR will be summarized using Kaplan Meier method and displayed graphically. Median DOCR and 2 sided 95% CI will be provided.

### **Progression-free Survival**

PFS is defined as the time from the date of first dose until confirmed PD per IMWG criteria or death due to any cause, whichever occurs first.

PFS will be censored as follows:

- For participants who do not have an event (PD per IMWG criteria or death due to any cause), censoring will occur on the date of the last adequate disease assessment;
- For participants who start a new anticancer therapy prior to an event, censoring will occur on the date of the last adequate disease assessment before the new anticancer therapy;
- For participants with an event after a gap of 2 or more missing disease assessments, censoring will occur on the date of the last adequate disease assessment before the gap;
- Participants who do not have an adequate post-baseline disease assessment will be censored on the date of first dose of study intervention unless death occurs on or before the time of the second planned disease assessment (ie,  $\leq 8$  weeks after the date of first dose) in which case the death will be considered an event.

PFS will be summarized using Kaplan Meier method and displayed graphically. Median PFS and 2-sided 95% CI will be provided.

### **Overall Survival**

OS is defined as the time from the date of first dose until death due to any cause. Survival status is expected to be collected irrespective of study intervention discontinuation or

participant's request to discontinue study procedures. All participants who have not withdrawn consent for further participation in the study should be followed for survival until the end of the study. OS for participants not known to have died are censored on the date of last known alive.

OS will be summarized using Kaplan Meier method and displayed graphically. Median OS and 2-sided 95% CI will be provided.

### **Time to Response**

TTR is defined, for participants with an objective response per IMWG criteria, as the time from the date of first dose to the first documentation of objective response that is subsequently confirmed.

TTR will be summarized using mean, standard deviation, minimum, median, and maximum.

CCI

### **9.3.3.3. Pharmacokinetic Analyses**

PK data analyses will include descriptive summary statistics of the predose and postdose serum concentrations of eh-anatamab by cohort, study visit and time point. In addition, the PK data from this study may be pooled with other studies to develop a population PK model. The correlation between eh-anatamab  $C_{max-24}$  after the first step-up dose (ie, 4 mg) and the probability of All Grade and Grade 2 and higher CRS will be evaluated; other relevant PK metrics may be explored. The results of these analyses correlating eh-anatamab exposure to probability of CRS will be reported in the clinical study report or a separate modeling report. The correlations between eh-anatamab exposure parameters and pharmacodynamic biomarker including cytokine data, efficacy and/or other safety outcomes will also be explored. The results of these modeling analyses may be reported separately from the clinical study report.

### **9.3.3.4. Immunogenicity Analyses**

For immunogenicity data, the percentage of participants with at least one positive, post dose ADA will be summarized. Listings and summary tabulations of the ADA data at baseline and post-first dose will be generated. Samples testing ADA positive will also be analyzed for the presence of NAb, and results will be similarly summarized. For participants with positive ADA or NAb, the magnitude (titer), time of onset, and duration of ADA or NAb response will also be described. The potential impact of immunogenicity on PK and clinical response

including pharmacodynamic markers, safety/tolerability and efficacy will be explored, if warranted by the data.

CCI

